6.3. Investigational device(s) and comparator(s)

The study will collect data to calibrate and validate the performance of the Masimo Rad-G with Temperature as compared to [REDACTED] measurements.

6.4. Participants

Inclusion Criteria

- Patients age \geq 1 year old
- Febrile at time of enrollment: $\geq 99.5^{\circ}\text{F}/37.5^{\circ}\text{C}$ for sublingual temperature reference; $\geq 100.4^{\circ}\text{F}/38^{\circ}\text{C}$ for temporal artery temperature reference.
- English- or Spanish-speaking patient or parent/LAR

Exclusion Criteria

- Patients deemed not suitable for the study at the discretion of the investigator
- Patients who are rated as a 1 or 2 Emergency Severity Index

6.5. Procedures

6.5.1. Recruitment and Pre-Screening

The principal investigator or delegated study personnel will screen for potential febrile participants in triage and/or review EMR current vital signs records for febrile participants in the emergency department. Patients who meet inclusion and exclusion criteria will be enrolled in the study.

6.5.2. Consenting and Screening

Per FDA Guidance “IRB Waiver or Alteration of Informed Consent for Clinical Investigations Involving No More than Minimal Risk to Human Subjects” issued on January 2017, waiver of documentation of informed consent for certain FDA-regulated minimal risk clinical investigations will facilitate investigators’ ability to conduct studies that may contribute substantially to the development of products to diagnose or treat diseases or conditions, or address unmet medical needs. The IRB can waive the requirements to document informed consent when the IRB finds that:

- The clinical investigation involves no more than minimal risk (as defined in 21 CFR 50.3(k) or 56.102(i)) to the subjects;
- The waiver or alteration will not adversely affect the rights and welfare of the subjects;
- The clinical investigation could not practicably be carried out without the waiver or alteration;
- Whenever appropriate, the subjects will be provided with additional pertinent information after participation

This study meets all the criteria listed by the FDA above and involves no more than minimal risk to the study participants because (1) the device under study is non-contact and (2) the clinical data to be obtained includes data collected for routine clinical use. The waiver is not expected to adversely affect the rights and welfare of the study participants because the study involves no-touch procedures and all data to be collected will be protected as outlined in the data collection and storage procedures. The clinical investigation could not practicably be carried out without the waiver due to the timing of the clinical assessment and immediate treatment of febrile conditions with antipyretics for children and adolescents in the Emergency Department.

After a caregiver/patient or their parent/LAR checks into the Emergency Department, a nurse or trained study investigator will approach them, and ask if they would like to participate in a short study looking at fever. If the patient or their parent/LAR is interested, an informational sheet outlining the study will be provided to them. This Study Information Sheet will be available in English and Spanish, the two most common languages in Orange County, California. The information sheet will be provided prior to the start of the study to inform the patient and/or their parent/LAR about the study and what data will be collected. Content on the information sheet will include: (1) research purpose and procedures, (2) risks, (3) benefits, (4) confidentiality, (5) whom (and how) to contact study personnel, (6) the voluntary nature of human research and the ability to withdraw participation, and (7) reporting of significant new findings. If the participant or their parent/LAR verbally agrees, they will be considered enrolled in the study. Verbal consent from the study investigator will be collected after review of the information sheet. Reasonable and appropriate protections will be implemented so that risks related to invasion of privacy and breach of confidentiality is no greater than minimal. After having the opportunity to review the information sheet, study participants or their parent/LAR will have the opportunity to decline participation in the study. After participants have verbally consented, they will be entered into the study system and study procedures outlined in the protocol will proceed.

HIPAA Waiver for Participant Screening

The screening of participants will require the investigators to access personal health information to identify prospective participants without HIPAA authorization. The participants’ rights and welfare will not be adversely affected by waiving HIPAA authorization. This protected health information will not be inappropriately reused or disclosed to any other person or entity. To further safeguard all protected health information, the data will not be labeled with any personal identifying information. Also, the data will not be stored with any protected health information identifiers.

6.5.3. Data Collection Procedure

6.5.3.1. Data collected by the Rad-G with Temperature is not intended to be used for clinical decisions, and research personnel should continue to use standard of care procedures for monitoring participants.

6.5.3.2. Study duration will be approximately 15 to 30 minutes.

6.5.3.6. Record start and end time of data collection procedures on the CRF.

6.5.3.7. Take the screening temperature measurement using the same thermometer to be used for the reference measurements, immediately before beginning the study measurements. The subject should be withdrawn from the study if they do not meet the criteria for temperature [REDACTED]

Reference Measurements

Multiple reference measurements may be obtained.

6.5.3.12. The three measurements need to be taken in quick succession of each other, with approximately 3 seconds between each measurement

6.5.3.13. Be sure to keep the Rad-G device steady during the measurement.

6.5.3.15. In the validation phase, [REDACTED] measurements will be obtained per subject.

6.5.3.16. Data from the Rad-G with Temperature device will be downloaded using Masimo [REDACTED] software on the data collection laptop at the end of each day. Reference data [REDACTED] will be downloaded to the data collection laptop using a USB flash drive.

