1. OVERALL SYNOPSIS OF THE CLINICAL INVESTIGATION

Clinical investigation title:	Calibration and Validation of the Masimo Rad-G with Temperature device in Febrile Patients
Study objective(s):	The objective of this study is to gather temperature data using the Masimo Rad-G with Temperature for calibration and validation purposes.
Investigational device(s):	Masimo Rad-G with Temperature
Number of participants:	Up to 250 participants.
Inclusion criteria:	
Participant age \geq 1 year oldFebrile at time of enrollment: \geq 99.5°F/37.5°C for sublingual temperature reference; \geq 100.4°F/38°C for temporal artery temperature reference.English- or Spanish-speaking patient or parent/Legally Authorized Representative (LAR)
Exclusion criteria:	
Participants deemed not suitable for the study at the discretion of the investigatorPatients who are rated as a 1 or 2 Emergency Severity Index
Duration of the clinical investigation:	The expected duration of study enrollment is 1 to 3 months.
Study endpoint(s):	For the validation phase of the study, accuracy of temperature measurements using the Masimo Rad-G with Temperature will be compared to reference temperature measurements.

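### Does confirming fever with the reference thermometer itself (section 6.5.3.7) bias the Rad-G minus reference difference enough to require a change?

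*Combined protocol and SAP*

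**What the plan says.** Selection happens twice. Under section 6.5.1, staff "screen for potential febrile participants in triage and/or review EMR current vital signs records for febrile participants in the emergency department". Section 6.5.3.7 then adds a confirmatory reading: "Take the screening temperature measurement using the same thermometer to be used for the reference measurements, immediately before beginning the study measurements". The rule that follows is "The subject should be withdrawn from the study if they do not meet the criteria for temperature", and the rest of that sentence is redacted.

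The entry limits in sections 1 and 6.4 are lower bounds that depend on the reference type: "99.5°F/37.5°C for sublingual temperature reference" and "100.4°F/38°C for temporal artery temperature reference". Fever is required at the time of enrolment. One set of criteria is shown for both the calibration and the validation group.

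Reference readings have their own heading in section 6.5.3, after the screening step, with the note "Multiple reference measurements may be obtained". The visible text does not say that the screening value is used as a reference value. The validation endpoint in section 1 is that "accuracy of temperature measurements using the Masimo Rad-G with Temperature will be compared to reference temperature measurements". Section 7.3 takes its minimum of 32 febrile patients from an ISO standard.

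**The concern.** A reading clears a lower limit either because the patient is hot or because the thermometer reads high in that patient. Keeping only those who clear it therefore favours positive reference error. If that error comes from site, technique, perfusion or mouth breathing, it will probably still be present in reference readings taken moments later with the same instrument. The retained reference would then average too high and Rad-G minus reference too low.

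Two features add to the worry. Patients have already been found febrile at triage or in the record, so the second cut can look unnecessary. Calibration and validation patients also appear to be selected alike. A device calibrated to a reference that reads high would over-read in unselected use, and a validation group selected in the same way could not show it.

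**Working it through.** **Inputs.** From the documents: cuts of 37.5 °C (sublingual) and 38 °C (temporal artery), and a minimum of 32 validation patients. The visible text gives no SD, margin or power, so the 32 cannot be reproduced by calculation. Every temperature mean, SD and correlation below is an assumption.

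**Step 1: one cut.** Let the screening reading be S = T + B + e. T is true temperature (SD 0.7 °C), B is reference error that persists within the patient (SD b), and e is independent reading noise. The device is taken as unbiased for T, and patients are kept if S ≥ cut. With s = √(0.7² + b² + e²), where e is now the noise SD, a = (cut − mean)/s and λ = φ(a)/(1 − Φ(a)):

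- separate reference readings: mean difference = −(b²/s)λ;
- screening value reused as the reference: mean difference = −((b² + e²)/s)λ.

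Example with the mean at the cut and b = e = 0.2: s = √(0.49 + 0.04 + 0.04) = 0.755 and λ = 0.798, so the shift is −(0.04/0.755) × 0.798 = −0.042 °C. With b = 0 and separate readings it is exactly 0. The same thermometer is therefore not enough; the error must persist.

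For b from 0.1 to 0.3 with separate readings:

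| Mean true temperature relative to cut | Shift (°C) |
|---|---|
| 1.0 above | −0.002 to −0.023 |
| 0.5 above | −0.006 to −0.051 |
| at the cut | −0.011 to −0.091 |
| 0.5 below | −0.018 to −0.142 |

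For scale, the standard error of a mean difference at n = 32 is SD/√32: 0.035, 0.053 or 0.088 °C for an assumed SD of 0.2, 0.3 or 0.5 °C.

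**Step 2: both cuts.** What matters for section 6.5.3.7 is how much it adds to triage selection. Take T as N(37.2, 0.7) or N(37.5, 0.8), persistent SD 0.2 to 0.4, reading noise 0.1, and correlation ρ between persistent error at triage and in the study reference. Simulation with 4 million patients per setting, 38 °C cut, gives this mean reference error among those kept (°C):

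| ρ | Triage cut only | Both cuts | Added by 6.5.3.7 |
|---|---|---|---|
| 0 | 0.00 | 0.03 to 0.19 | 0.03 to 0.19 |
| 0.5 | 0.03 to 0.15 | 0.05 to 0.26 | 0.02 to 0.11 |
| 0.9 | 0.05 to 0.27 | 0.06 to 0.30 | 0.006 to 0.035 |
| 1.0 | 0.06 to 0.30 | 0.06 to 0.31 | 0.003 to 0.012 |

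The triage-only column agrees with ρ(b²/s)λ. For N(37.2, 0.7) and b = 0.4, s = √(0.49 + 0.16 + 0.01) = 0.812, a = 0.8/0.812 = 0.985 and λ = 1.513, giving ρ × (0.16/0.812) × 1.513 = 0.298ρ.

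At the 37.5 °C cut with N(37.5, 0.8), the addition is 0.02 to 0.09 °C at ρ = 0, 0.004 to 0.02 °C at ρ = 0.9 and 0.002 to 0.008 °C at ρ = 1.

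**Step 3: which ρ?** The sources that make B persist mostly belong to the patient. They would tend to recur at triage if a similar thermometer is used there. Section 6.2 lists a hospital standard-of-care thermometer among the reference equipment, so this is plausible, though its type is redacted. The conditions that make B large thus also tend to raise ρ, and most of the bias then arises at triage.

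**Step 4: would measuring everyone help?** Suppose triage-qualified patients below the cut were measured too, and only those at or above it counted toward the 32. The febrile subset would still be defined by the same cut on the same thermometer, so its bias would be unchanged.

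**The case for a change.** The strongest case for a change is that the same patient, instrument and moment are where persistent error is most likely. Having none would require no patient-level reference error at all. At ρ = 0 the upper figure, 0.19 °C, is more than twice the largest standard error above (0.088 °C). At ρ of 0 or 0.5 the second cut would withdraw 14% to 43% of triage-febrile patients. One extra non-contact round in patients who have already agreed costs little and would make the effect visible. Reusing the screening value as a reference would be worse, up to −0.269 °C in Step 1 with b = e = 0.3 and the mean 0.5 °C below the cut.

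The mechanism and the arithmetic stand. Three things limit the case:

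- The large figures pair substantial persistent error with triage error unrelated to it, and with a population mean 0.5 to 0.8 °C below the cut.
- Extra rounds would describe patients who miss the criterion of fever at enrolment. A triage or record value may be out of date, and section 6.5.2 itself mentions immediate antipyretic treatment. Confirming current fever is a reasonable use of the reading.
- Nothing visible suggests reuse. Several steps of section 6.5.3 and parts of section 7 are not shown, so the lack of an explicit prohibition cannot be held against the plan.

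**Conclusion.** No change follows. The step may leave the retained reference slightly high, but it cannot be said to do so on the documents. With an assumed persistent SD of 0.2 to 0.4 °C, its addition to triage selection runs from about 0.002 °C (fully shared triage error, 37.5 °C cut) to 0.19 °C (independent triage error, 38 °C cut). It is zero if no error persists and the reference readings are separate.

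The sign in the validation data is also open. If the calibration group passed the same cut, calibration may absorb the shift and the validation difference would not show it; the calibration details are redacted.

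This is a fair trade-off: the plan accepts a possible selection effect of unknown size in return for confirming current fever on the scale that defines eligibility. Analysts can report how many patients were withdrawn at this step and plot the difference against distance from the cut, using reference readings separate from the screening value. That would be useful description and would leave the febrile-set result as it is.

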6.6. Monitoring plan

As the sponsor of this clinical investigation, Masimo Corporation is required by 21 CFR Part 812, of the Food and Drug Administration regulations to monitor and oversee the progress of the investigation. The monitor(s) assigned by Masimo Corporation to this task will be trained on departmental SOPs on conduct and monitoring of sponsored studies.

In accordance with good clinical practices guidelines, there will be at least three scheduled monitoring visits to ensure overall regulatory compliance of the study:

- An initiation visit, prior to any participant enrollment to confirm site readiness, and to document training on the study protocol and procedures, and use of equipment.
- At least one monitoring visit during initial enrollment, and/or every 2-4 weeks until completion of the study.
- A final close out visit after the last patient had finished the study.

The monitor will contact and visit the investigator and will be allowed, on request, to have access to all source documents needed to verify the entries in the CRFs and other GCP-related documents (IRB approvals, IRB correspondences, and ICFs) provided that participant confidentiality is maintained in agreement with HIPAA regulations.

It will be the monitor's responsibility to inspect the CRFs at regular intervals throughout the study, to verify the adherence to the CIP and the completeness, consistency and accuracy of the data being entered on them.

During each visit, the monitor will also verify adherence to the inclusion/exclusion criteria, and documentation of SAEs/SADES and protocol deviations/violations, and check CRF against source documentation.

After each visit, the monitor will provide a monitoring letter to the investigator within 4 weeks of visit completion. The monitoring letter will detail findings and open action items observed during the visit. It is the responsibility of the Principal Investigator and Study Coordinator(s) to respond to the findings of the monitoring letter and complete any open action items as soon as possible but no later than 60 days of receiving the monitoring letter. Any open action items not completed within the time allowed may be sufficient grounds for study site suspension or termination; it will be up to the sponsor to determine whether any incomplete action items are sufficient grounds for suspension or termination. Depending on the quality of the data and/or changes to factors affecting patient safety, additional monitoring visits may be necessary according at the sponsor's discretion.

7. STATISTICAL DESIGN AND ANALYSIS

7.1. Acceptance Criteria

7.3. Sample Size

The [REDACTED] minimum of 32 febrile patients for the validation phase per ISO 80601-2-56:2017, section 201.102.

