6. DESIGN OF THE CLINICAL INVESTIGATION

6.1. General

This is a prospective, nonrandomized, single arm study. Temperature data will be obtained using the Masimo Rad-G with Temperature while obtaining [REDACTED]

There will be up to 250 participants enrolled into this study, divided into two groups: calibration and validation. [REDACTED]

[REDACTED] The second group will be the validation set that will be used to evaluate study objectives.

[REDACTED] For the validation phase of the study, accuracy of temperature measurements using the Masimo Rad-G with Temperature will be compared to [REDACTED]

The validation of the accuracy of the temperature measurement in the investigational device may be determined using data collected from this study, in addition to data from other Masimo sponsored studies.

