7.5. Expected Dropout Rates

Participants may not complete the study for various reasons, at the investigator's or study staff's discretion, or because the participant or participant's parent/LAR does not want to continue the study. Due to the short duration and simple, noninvasive procedures of this study, there are limited expected dropouts.

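### Could the validation phase end with fewer than the 32 febrile patients that section 7.3 requires?

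*Combined protocol and SAP*

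**What the plan says.** Section 7.3 requires a "minimum of 32 febrile patients for the validation phase per ISO 80601-2-56:2017, section 201.102". The words just before this are redacted, so the verb that would tell us whether the 32 are enrolled, measured or analysed cannot be read.

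Four places bear on when a patient enters the count:

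- Section 6.4 lists as an inclusion criterion "Febrile at time of enrollment".
- Section 6.5.1 has staff "screen for potential febrile participants in triage and/or review EMR current vital signs records for febrile participants in the emergency department", and then says "Patients who meet inclusion and exclusion criteria will be enrolled in the study".
- Section 6.5.2 says "If the participant or their parent/LAR verbally agrees, they will be considered enrolled in the study".
- Section 6.5.3.7 has a screening temperature taken with the reference thermometer just before the study measurements, and adds "The subject should be withdrawn from the study if they do not meet the criteria for temperature". The rest of that step is redacted.

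Section 7.4.1 then removes whole subjects from the analysis on four grounds: antipyretics given during participation, no complete round of measurements, data suggesting a faulty device or sensor, and data suggesting outside interference. Section 7.5 gives no loss rate and says only that "there are limited expected dropouts". Section 6.1 sets the ceiling: "There will be up to 250 participants enrolled into this study, divided into two groups: calibration and validation".

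**The concern.** Read in order, these sections appear to count a patient before fever is confirmed, then withdraw some patients, then exclude others, with no visible allowance for either loss. If the validation phase closed once 32 patients had agreed to take part, a single withdrawal or exclusion would leave the analysis below the number that the plan attributes to its standard. Section 7.4 takes the analysis procedure from the same section of that standard, so falling short would weaken the claim of conformity. Two of the four exclusions also rest on judgement about what the data suggest. Near a count of 32, those judgements could decide whether the minimum was met.

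**Working it through.** **The plan's own figure.** The 32 is taken from an external standard. No standard deviation, acceptance limit, error rate or power is visible, so it cannot be re-derived from the documents. It is taken as given.

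**Inputs.** Minimum 32 (section 7.3) and ceiling 250 over both phases (section 6.1). The combined loss rate *d* is an assumption, because the documents give none. The range used is 2% to 30%.

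**If exactly 32 are enrolled.** The chance that all 32 are analysed is (1 − d)^32, and the expected number analysed is 32 × (1 − d). The enrolment needed for 95% assurance is the smallest N with P(Binomial(N, 1 − d) ≥ 32) ≥ 0.95.

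| Assumed loss d | Chance all 32 analysed | Expected analysed of 32 | N for 95% assurance of 32 |
|---|---|---|---|
| 2% | 52.4% | 31.4 | 34 |
| 5% | 19.4% | 30.4 | 36 |
| 10% | 3.4% | 28.8 | 39 |
| 15% | 0.55% | 27.2 | 42 |
| 20% | 0.08% | 25.6 | 46 |
| 30% | below 0.01% | 22.4 | 53 |

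The second and third columns hold only if enrolment stops at 32. The last column shows how little extra enrolment removes the problem.

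**Room under the ceiling.** At 30% loss, 53 validation patients suffice, which leaves 250 − 53 = 197 places for calibration. The split between phases is not visible. If half, 125, went to validation (an assumption), the expected analysed number would fall below 32 only if losses exceeded 1 − 32/125 = 74.4%.

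**What falling short costs in precision.** Take one value per subject and a 95% interval for the mean difference, with half-width t(0.975, n − 1)/√n in SD units. For n = 32 this is 2.040/5.657 = 0.361. For n = 29, about what a 10% loss leaves, it is 2.048/5.385 = 0.380. The interval is about 5% wider (0.380/0.361 = 1.05).

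**Which losses count against the 32.** Section 7.3 counts febrile patients. Someone withdrawn under 6.5.3.7 for not meeting the temperature criterion is not naturally one of them, so that withdrawal does not reduce a count of 32 febrile patients. Fever has also been looked for in triage or the record before approach (6.5.1), so the later reading is a confirmation with the reference thermometer. Only the four exclusions in 7.4.1 remain as a route to a shortfall. The single rate *d* in the table lumps both routes together and so overstates the relevant loss for any given total.

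**When a shortfall would be noticed.** A session lasts about 15 to 30 minutes (6.5.3.2), and device data are downloaded at the end of each day (6.5.3.16). Antipyretic use and incomplete rounds are known at the bedside. The data behind the other two exclusions are in hand the same day. The team can therefore see the usable count while recruitment is still open.

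**The case for a change.** The best case for a change runs as follows. A ceiling obliges nobody to continue past 32, and it is shared with calibration. The plan itself points to one source of loss: section 6.5.2 justifies the consent waiver by the prompt use of antipyretics in children and adolescents in the emergency department, and 7.4.1 excludes anyone given them during participation. Section 6.1 also lets validation draw on other sponsor studies, without visible word on whether those subjects count towards the 32. One sentence in 7.3 would settle the matter at the cost of a few short sessions.

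Part of this stands. No visible sentence says that the 32 are counted after exclusions, and sections 6.4, 6.5.1, 6.5.2 and 6.5.3.7 do not agree on the moment of enrolment. The rest is weaker. The waiver is sought so that measurement can fit around early treatment, and the antipyretic exclusion covers only a session of 15 to 30 minutes. That the ceiling does not compel further enrolment does not mean the sponsor would stop at 32 with unusable subjects among them. The differing enrolment wording affects how a withdrawn patient is labelled, not how many febrile patients are analysed. Redefining enrolment would also cost more than a sentence: it changes who is recorded as enrolled on a case report form (8.3) and needs an amendment approved by the IRB (9 and 12). Pressure on the judgement-based exclusions is conjecture here, and how those exclusions are defined is a separate question from the count.

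**Conclusion.** The concern does not call for a change. The arithmetic is right, but it describes a trial that stops at exactly 32 and loses patients at rates that the documents do not give. No stated rule produces a wrong number. What is left is a counting convention that cannot be read in the published text, partly because the start of the 7.3 sentence is redacted. A team working to a minimum of 32 febrile patients would count usable ones and recruit a few more if needed: 34 to 53 enrolled for 95% assurance at assumed losses of 2% to 30%, well inside 250. If it did finish at 29, precision would hardly move (0.36 to 0.38 SD, assuming one value per subject). The mismatch over the moment of enrolment is a clerical slip with no effect on the analysis. This conclusion assumes that validation enrolment is not fixed at 32 in the redacted text. The content of the cited standard was not available and was not used.
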